3.3.5 Technical Success

The residual stenosis rate after initial treatment is defined as less than 30%.

The residual stenosis rate is calculated using the following formula.

$$\text{Residual stenosis rate (\%)} = \frac{\text{Standard diameter} - \text{Diameter of stenosis part}}{\text{Standard diameter}} \times 100$$

The definitions of diameter of stenosis part and standard diameter are as follows.

Diameter of stenosis part: Diameter of the narrowest part after deployment of the device

Standard diameter: Diameter of the part without stenosis in the area near the stenosis

3.3.6 Clinical Success

It is defined as resumption of one or more normal dialyses after initial treatment with this device.

3.4 [REDACTED]
[REDACTED]

3.4.1 BMI

[figure not shown]
It is calculated using the following formula.

$$\text{BMI}[\text{kg}/\text{m}^2] = \text{Weight}[\text{kg}] \div (\text{Height}[\text{cm}] / 100)^2$$

[figure not shown]
3.4.2

Term	Percentage
GMOs	75%
Organic	85%
Natural	80%
Artificial	70%
Organic	85%
Natural	80%
Artificial	70%
Organic	85%
Natural	80%
Artificial	70%
Organic	85%
Natural	80%
Artificial	70%

3.4.3

3.4.4

3.4.5

4. Cases and Data Handling

4.1 Case Handling

The analysis population is defined as follows.

Analysis population	Definition
Enrolled patients	All patients enrolled
Patients with completed study form	Patients with at least one item entered in the study form

Analysis population	Definition
Patients for each period (at the time of treatment, at 1-month – 24-month)	Patients with at least one item entered in the study form for each period
Patients with the fixed study form for each period	Patients with completion of DM review as specified in the data management plan of study form for each period.
Patients with the unfixed study form for each period	Patients with at least one item entered in the study form for each period, but DM review not completed.
[REDACTED]	[REDACTED]
[REDACTED]	[REDACTED]
[REDACTED]	
[REDACTED]	

4.2 Handling of missing values

4.2.1 Data Complements

For missing data, data complements are not performed.

4.2.2 Missing continuous quantity

In cases of missing data in aggregate calculation of continuous quantities, they are excluded from the aggregate calculation.

4.2.3 Nominal scale, Ordinal scale

- If there is an entry of unknown, handle it as “Unknown”
- If an analysis is performed with unfixed data, the data that have not been collected are treated as “Not described”.
- In cases of an item that allows multiple answers, if all the items are not selected, it is classified as “Not described”.
- Included in the denominator of percentage unless otherwise noted.
- “Unknown” and “Not described” are excluded from the test.

4.2.4 Date Variables

If year is known but month and date are unknown, “01” is applied to each month and date for the aggregate calculation. If year is unknown or date is unrecognizable, handle it as unknown.

However, if the onset date of an adverse event or a device deficiency is before the date of initial procedure as a result of above complements, the same date as the date of the initial procedure is to be complemented.

4.3 Handling of Safety Data

4.3.1 Handling of Adverse Event/ Device Deficiency

4.3.1.1 Number of Onset Patients

If multiple adverse events (device deficiencies for the aggregate calculation of device deficiencies) occur in the same patient, they are counted together as one case.

4.3.1.2 Aggregation method for the same patient and the same adverse event

4.3.1.2.1 Aggregate calculation of the number of patients

If the same adverse event (device deficiencies for the aggregate calculation of device deficiencies) occurs in the same patient, aggregate it together. In the case of periodic aggregate calculation, aggregate the data for each period.

4.3.1.2.2 Aggregate calculation of cases

Aggregate all events without grouping them together. In cases of periodic aggregate calculation, aggregate by time of onset date.

4.4 Handling of data over time

4.4.1 Calculation of the number of days

In this statistical analysis plan, the calculation of the number of days is unified by the following calculation method.

Strat n day = Subject date – Date of Procedure

Therefore, Start day is Start 0 day, the day after the start is Start 1 day, and the day before the start is Start -1 day.

4.4.2 Adoption Range of Time Period

The data for each evaluation period is adopted from the adoption range specified in the table below.

4.4.2.1 Adoption Range for Adverse Event/Device Deficiency

Follow-up window	Classification of Adoption Range
Day of Procedure	Day 0
1 month	Day 1 \leq Day 37
3 months	Day 38 \leq Day 121

6 months	Day 122 \leq Day 212
12 months	Day 213 \leq Day 395
24 months	Day 396 \leq Day 760
Over 24 months	Day 761 \leq

4.4.2.2 Adoption Range of the number of patients for the study of adverse events/device deficiency

For the period other than “the date of procedure”, calculate the latest date – date of procedure, and the number of target patients is defined as those meeting the following criteria: Latest date is that among the “Latest follow-up date”, “Latest onset date of adverse event”, “Latest onset date of device deficiency”, and “Latest date of implementing reintervention”.

Follow-up window	Classification of Adoption Range
Day of Procedure	Patients with procedure performed
1 month	1 \leq
3 months	38 \leq
6 months	122 \leq
12 months	213 \leq
24 months	396 \leq
Over 24 months	761 \leq

4.4.2.3 [REDACTED] Adoption Range of Reintervention

Period	Stipulated date	Classification of Adoption Range for reintervention
1 month	30 days	Day 0 \leq Day 30
3 months	91 days	Day 0 \leq Day 91
6 months	183 days	Day 0 \leq Day 183
12 months	365 days	Day 0 \leq Day 365
24 months	730 days	Day 0 \leq Day 730

4.4.2.4 [REDACTED] Adoption Range of Kaplan-Meier Estimate

Period	Classification of Adoption Range
0 day	Day 0
1 month	Day 1 \leq Day 30
3 months	Day 31 \leq Day 91
6 months	Day 92 \leq Day 183

12 months	Day 184 \leq Day 365
24 months	Day 366 \leq Day 730

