## 9.2 Safety endpoint

- (1) Incidence of device and procedure-related adverse events at treatment and up to 30 days after treatment.
- (2) Incidence of adverse events and device defect in each follow-up period

The definitions of adverse events and failures in this surveillance are as follows.

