### **9.2.1 Collection period for adverse events and device defect**

From the time of treatment to the end of the surveillance (24 months or discontinuation of the study). The time of treatment with Viabahn should be the time of initial treatment.

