3.3.1 Events of Primary Patency of Target Lesions and Termination

Primary patency of a target lesion is defined as the period after index procedure until reaching one of the following conditions at the earliest.

Event	EDC item	Date of Event
Occlusion of VIABAHN	Answer to “Did the device implanted in a treated lesion maintain patency? ([REDACTED]) ” is “Loss of patency ([REDACTED])	Date of follow-up ([REDACTED])

Event	EDC item	Date of Event
	Enter “Occlusion of VIABAHN” in “Adverse Event ([REDACTED])”	Date of onset ([REDACTED])
Conduct reintervention	“Purpose of reintervention ([REDACTED])” is “Patency of the initial implanted device ([REDACTED])”	Date of reintervention ([REDACTED])
Discontinuation of study	Answer to “Did conduct follow-up ([REDACTED])” is “Discontinuation ([REDACTED])” and “Reason for discontinuation ([REDACTED])” is “Other (discontinuation of use of the device, etc. ([REDACTED]))”	Date determined to be discontinued ([REDACTED])
	Answer to “Did complete the study? ([REDACTED])” is “Discontinuation ([REDACTED])” and “Reason for discontinuation ([REDACTED])” is “Other (discontinuation of use of the device, etc. ([REDACTED]))”	Date determined to be discontinued ([REDACTED])

In addition, termination is defined as the latest of the following dates.

Termination	EDC Item	Termination date
Completion of study	Answer to “Did complete the study? ([REDACTED])” is “Completed ([REDACTED])” and to “Did the device implanted in a treated lesion maintain patency? ([REDACTED])” is “Patency ([REDACTED])”	Date of completion ([REDACTED])
Study ongoing	Date of procedure [REDACTED]	Date of procedure [REDACTED]
	Answer to “Did the device implanted in a treated lesion maintain patency? ([REDACTED])” is “Patency ([REDACTED])”	Date of follow-up ([REDACTED])

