- If a patient has multiple occurrences of the same SOC/PT at the same time, it is counted as one case in the case-counting. The number of cases is not summarized, but all are counted.
- If a patient has multiple occurrences of the same SOC/PT at different time points, count one case at each time . The number of cases is not summarized, but counted at each time point.
- The denominator of incidence rate is the number of patients for the study. Refer to “4.4.2.2 Adoption Range of number of cases for study of adverse events/ device deficiency” for the calculation method for the number of patients for the study.
- The same analysis is performed for patients with On-Label use
- Analysis of the device and procedure-related adverse events and serious adverse events is conducted in a similar layout. Analysis is also conducted for adverse events, and adverse events and serious adverse events related to the device and the procedure similarly in the categories of under 65 years old/ 65 years old and older and under 75 years old/75 years old and older.

[figure not shown]
8.3 List of occurrences of device deficiency and infectious disease in post-marketing study, etc. (Appendix Form 3-3)

Title of Table : 8.3 List of occurrences of device deficiency and infectious disease in post-marketing study, etc. (Appendix Form 3-3)

[figure not shown]
Analysis object : Patients with completed study form

[figure not shown]
Contents of Analysis :

- The following analysis is performed for each category of “4.4.2.1 Adoption Range for Adverse Event / Device Deficiency”
- Calculate the overall numbers of sites, target patients, patients with device deficiency, and cases of device deficiency, as well as incidence of device deficiency
- Calculate the numbers of patients, incidence for each adverse device effect (or an infectious disease if it occurred) by the time of occurrence
- If a patient has multiple occurrences of the same device deficiency at the same time, it is counted as one case in the case-counting.
- If a patient has multiple occurrences of the same device deficiency at different time points, count one case at each time .
- If both known and unknown cases exist in the same event, they are counted as separate events, and the unknown event is presented first
- An unknown event is indicated by prefixing the event name with “*”

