- The denominator of incidence rate is the number of patients for the study. Refer to “4.4.2.2 Adoption Range of number of patients for study of adverse events/ device deficiency” for the calculation method for the number of patients for the study.

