9.5 List of Mortality Cases

Title of Table : 9.5 List of Mortality cases

1

Analysis object : Enrolled patients

Contents of Analysis : • Show the cause of death, days to death, causal relationship, course of occurrence, details of treatment for each patient who “Died” as the outcome of an adverse event. In addition, the following items on the study form are shown.

- Cause of death: Name of adverse event
- Causal relationship: Causal relationship judgement
- Course of occurrence: Course of occurrence of adverse event
- Treatment: Treatment for adverse event

The day to death is defined as the number of days from the date of the procedure to the date of outcome of the adverse event (Date of outcome of the adverse event – Date of procedure).

10. References

Nothing in particular

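### The safety denominator in SAP 4.4.2.2 ignores how long each patient was observed in a window, so the 24-month incidence in tables 8.2 and 8.3 is modestly off, usually too low

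*SAP*

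**What the plan says.** Protocol 9.2 lists as its second safety endpoint "Incidence of adverse events and device defect in each follow-up period". Protocol 9.2.1 sets the collection period: "From the time of treatment to the end of the surveillance (24 months or discontinuation of the study".

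SAP 4.4.2.1 assigns events to windows by onset day; the 24-month window is Days 396-760, and an *Over 24 months* row starts at Day 761. SAP 4.4.2.2 then decides who is counted in each window. After the day of the procedure, a patient is counted if the latest date, in days from the procedure, is at or beyond the window's lower bound (396 for 24 months). On which dates qualify, it says "Latest date is that among the “Latest follow-up date”, “Latest onset date of adverse event”, “Latest onset date of device deficiency", and it adds the latest reintervention date. There is no upper bound and no requirement for time observed.

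SAP 8.1, 8.2 and 8.3 all use this count: "The denominator of incidence rate is the number of patients for the study", with a reference back to 4.4.2.2. SAP 8.2 extends the table: "The same analysis is performed for patients with On-Label use". It also repeats it for related and serious events and for two age splits.

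The visible text does not define *Latest follow-up date*. SAP 3.3.1 shows discontinuation entered under the item "Did conduct follow-up", yet with a date of its own, "Date determined to be discontinued", separate from the date of follow-up.

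**The concern.** A crude proportion gives every patient in the denominator the same weight, as if all had the same chance of showing an event in the window. Here they do not, for two reasons that pull in opposite directions.

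- **Part-observed patients.** Protocol Table 2 accepts a 12-month visit up to Day 455. A patient seen on schedule on Days 396-455 and then lost is in the 24-month denominator with at most 60 days observed by that visit. A completer seen at Day 640, also on schedule, has 245 of 365 days. Both count as one. This lowers the incidence.
- **Admission by an event.** If *Latest follow-up date* means visits only, take two patients seen on Day 365 and lost on the same later day before the 24-month visit. The one with an event on or after Day 396 is counted; the event-free one is not. Numerator and denominator are then linked, which raises the incidence. If the discontinuation contact counts as follow-up, both patients are in and this effect vanishes, but more part-observed patients enter.

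At stake is the late-window figure for a protocol safety endpoint, and the chance that two programmers reading the same sentence produce different tables.

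**Working it through.** The visible text gives no expected incidence or loss rate, so there is no plan figure to reproduce.

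**Inputs from the documents.** 24-month window: Days 396-760, or 760 - 396 + 1 = 365 days. 12-month visit range: Days 275-455, or 181 days, of which 455 - 396 + 1 = 60 (33%) lie inside the 24-month window. 24-month visit range: Days 640-820. A visit at Day 640 gives 640 - 396 + 1 = 245 days (67% of the window). Target: 100 indicated cases.

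**Assumptions, not in the documents.** Constant event risk of 20% per year (10% and 40% as a check); loss of 0, 5, 15 or 30% per year, unrelated to events; visits either at Days 30/91/183/365/730 or uniform over Table 2; events observed until loss or completion.

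**Chance of showing a first event in the window, by days observed,** 1 - 0.8^(d/365):

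- 60 days: 3.6%
- 245 days: 13.9%
- 335 days (completion at Day 730): 18.5%
- 365 days: 20.0%

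**Worked case: visits at nominal days, 15% yearly loss.** Take everyone still observed at Day 396. Event rate a = -ln 0.80 = 0.2231 per year; loss rate b = -ln 0.85 = 0.1625 per year; time T = 335/365 = 0.918 years.

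- Observed to have an event: a/(a+b) × (1 - exp(-(a+b)T)) = 0.5786 × 0.2981 = 0.1725
- Complete: exp(-bT) = 0.8614, of whom with an event 0.8614 × 0.1852 = 0.1595
- Lost, but with an event first: 0.1725 - 0.1595 = 0.0130
- Discontinuation contact counts: 0.1725/1 = **17.2%**
- Visits only: 0.1725/(0.8614 + 0.0130) = **19.7%**

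The true value for the window is 20.0%. At 30% yearly loss the same formulas give 15.9% and 21.3%. Under the visits-only reading, the share of affected patients who are in the denominator only because of their own event is 0.0130/0.1725 = 7.5% at 15% loss and 16% at 30%.

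**Simulation: 600,000 patients in each of 16 scenarios (two visit patterns, four loss rates, two readings).** Results for the 24-month window:

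| Yearly event risk | SAP rule | True, Days 396-760 |
|---|---|---|
| 10% | 7.6-10.7% | 10.0% |
| 20% | 15.4-21.3% | 20.0% |
| 40% | 31.5-41.8% | 40.0% |

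At 20% risk, 15 of 16 scenarios are low. The exception is nominal visits, visits only, 30% loss. With loss up to 15% per year the range is 16.7-19.8%.

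**Against sampling error.** The standard error is sqrt(t(1-t)/(100 × share in denominator)). With uniform visits, 15% loss and the contact counted, 84 of 100 patients are in the denominator, so sqrt(0.2 × 0.8/84) = 4.4 points. Those 84 carry about 69 full-window equivalents of observation. Over the 16 scenarios the error runs from -0.94 to +0.23 standard errors (-1.43 to +0.27 at 40% risk).

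**Other windows at 20% risk.** 1 month 2.15-2.28% (true 2.24%); 3 months 4.8-5.0% (5.0%); 6 months 5.2-5.5% (5.4%); 12 months 9.7-11.3% (10.6%).

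**Check of the remedy at 20% risk.** A rate per person-time over patients still observed at Day 396, converted by 1 - exp(-rate × 365), returns about 20% in every scenario. Kaplan-Meier for first event gives 1.8%, 19.9-20.1% and 35.9-36.1% at Days 30, 365 and 730 (true 1.8%, 20.0%, 36.0%).

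**The case against.** Counting patients who enter an interval is a common descriptive convention, and the SAP never claims that they were all observed to its end. Including event dates also ensures that every patient in the numerator is in the denominator. No test or decision rule is visibly attached to these tables, the size rests on assumed rates, and the two effects partly cancel. All of that stands. It argues for keeping the table, not for leaving it as the only safety estimate.

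Four stronger readings are tempting, and the documents do not support them.

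- **That ending the window at Day 760 is an error**, because collection ends at 24 months and SAP 4.4.2.3 and 4.4.2.4 use Day 730. The safety windows end 7, 30, 29, 30 and 30 days after the stipulated days 30, 91, 183, 365 and 730, which looks like a deliberate visit allowance. Table 2 accepts a 24-month visit up to Day 820, and the SAP has a row for later events. Days 365 and 730 in those two sections govern reintervention and Kaplan-Meier estimates, not adverse events.
- **That this rule is what stops the windows being compared.** They last 37, 84, 91, 183 and 365 days, so crude proportions would not be comparable even with complete follow-up.
- **That events certainly admit patients selectively.** This holds only if the discontinuation contact is left out. Recording discontinuation under the follow-up item makes the opposite reading plausible.
- **That no adjusted analysis is planned.** Much of SAP sections 7 to 9 is redacted, so a definition or an adjusted estimate may be there.

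**Conclusion.** The point holds as a modest flaw in a stated rule. Under either reading of *Latest follow-up date*, the 24-month incidence in tables 8.2 and 8.3 takes no account of unequal observation. At an assumed 20% yearly risk and 0-30% yearly loss it comes out at about 15.4-21.3% against 20.0%, usually low and within about one standard error at 100 patients. The extremes need 30% yearly loss. The undefined term alone moves the worked case from 17.2% to 19.7%.

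Day 0, the 1-month window and table 8.1 are essentially unaffected, and no conclusion reverses. The size depends on constant risk and on loss unrelated to events. Since death can be the outcome of an adverse event, real loss may not be so simple, and the good recovery by person-time should be read with that in mind. The change is worth making because it is cheap and bears on a protocol endpoint.

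**What to change.** In SAP 4.4.2.2:

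1. Define one end-of-observation date per patient: the earliest of completion, discontinuation and death, or the last follow-up contact if none of these is recorded. Apply it in the same way to patients with and without events.
2. State whether *Latest follow-up date* includes the discontinuation contact.
3. Keep the SAP's windows, including Day 760 and the *Over 24 months* row, and keep the existing tables, labelled as crude.
4. Beside the main 8.2 and 8.3 results, add events per 100 patient-years by window and a Kaplan-Meier or cumulative-incidence estimate of first event, for example at Days 30, 365 and 730.
5. List any event dated after end of observation.

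The cost is SAP wording and a small amount of extra tabulation; the subgroup repeats of 8.2 need not be duplicated. Completion, follow-up and discontinuation dates appear in SAP 3.3.1. The visible text shows the discontinuation date only for the reason category that counts as a patency event, so the sponsor should confirm that it is held for all reasons. Death has a date through SAP 9.5, which takes it from the record of the fatal event: "The day to death is defined as the number of days from the date of the procedure to the date of outcome".

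Where only the last visit date is available, some events will fall after it (2-16% of events in the 24-month window at 5-30% yearly loss, under the assumptions above). In that case show the rate with and without them.

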4.4.3 Day of Procedure

The date of the procedure is the date indicated in the “Procedural Information at the time of Treatment” section of the study form.

4.4.4 Age

Age is calculated as follows, using the full age at the date of the procedure, starting from the date of birth on the study form.

- ① Calculate the difference between the date and the date of birth
- ② If the date is before the date of birth, subtract 1 from the difference to obtain the full age.
If the date is the same as or later than the date of birth, the difference is taken as the full age.

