#### 3 Target number of cases and rationale for setting

Target number of cases : 100 cases (indicated cases)

Rationale :

[REDACTED]

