## **7 Planned surveillance period**

Total surveillance period : 4 years after obtaining approval

Preparation period : about 8 months

Enrollment period : about 6 months

Follow-up period : 24 months from procedure

Supplemental surveillance period, data fixed period, analysis period : about 10 months

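### The age rule's subtract-one condition can never be met and its difference has no unit; on a calendar-year reading, some patients are aged a year too old and a few cross the 65 and 75 cut-points

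*SAP*

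**What the plan says.** SAP 4.4.4 defines age at the procedure "using the full age at the date of the procedure, starting from the date of birth on the study form". The derivation has two steps.

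- Step 1: "Calculate the difference between the date and the date of birth". No unit is given.
- Step 2, first branch: "If the date is before the date of birth, subtract 1 from the difference to obtain the full age".
- Step 2, second branch: "If the date is the same as or later than the date of birth, the difference is taken as the full age".

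Neither step mentions a birthday or a comparison of month and day.

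Age is then used in SAP 8.2, where adverse event analyses, including those of related and serious events, are repeated "in the categories of under 65 years old/ 65 years old and older and under 75 years old/75 years old and older".

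The sections nearby do not settle the unit. SAP 4.4.1 says "the calculation of the number of days is unified by the following calculation method", which is a count of days from the procedure. SAP 4.4.5 (current smokers) and 4.4.6 (haemodialysis history) convert days to years by dividing by 365.25. SAP 4.4.4 has no such divisor.

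**The concern.** The subtraction is the only part of the rule that could turn a raw difference into completed years, and its condition compares the procedure date with the date of birth itself. The second branch therefore applies to everyone, and the raw difference becomes the age.

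If the raw difference is year of procedure minus year of birth, a patient born in October and treated in March is given the age they will reach that October. The error runs one way: patients aged 64 or 74 can be placed in the older group, and nobody is moved into a younger one. The age-split adverse event tables in SAP 8.2 would then hold a few patients, and any events they had, in the wrong column. The SAP is also what the age program is checked against, so a program with this fault would pass.

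**Working it through.** The documents state no age distribution and no counts by age group, so there is no figure of theirs to reproduce. The check asks what the rule returns under each reading of step 1.

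**Inputs from the documents**
- Target quantity: completed years at the procedure (SAP 4.4.4).
- Cut-points: 65 and 75 years (SAP 8.2).
- Enrolment: "Enrollment period : about 6 months" (Protocol 7), with no calendar months given.
- Size: 100 indicated cases, with other uses of the device also enrolled (Protocol 3 and 4).

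**Assumptions**
- Birthdays are uniform over the year, and procedures are uniform within the enrolment window.
- Ages are normal with mean/SD 70/10, 68/12 or 72/8.

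**1. How often the condition is met.** Procedure date before date of birth: 0% of patients. The uncorrected branch applies to 100%.

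**2. Readings of step 1**
- Calendar-year difference: one year too high for anyone treated before that year's birthday.
- Exact elapsed years, truncated: already the full age. Left fractional, it still puts everyone on the right side of 65 and 75. Step 2 is redundant either way.
- Days, as in SAP 4.4.1: the result is not an age in years.

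Only the first reading gives a subtract-1 step anything to do.

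**3. Share overstated under the calendar-year reading.** With uniform birthdays, the share treated before the birthday is 1 minus the mean position of the procedures in the year.
- January to June: 1 − 0.25 = 0.75
- April to September: 1 − 0.50 = 0.50
- July to December: 1 − 0.75 = 0.25

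A simulation of 200,000 patients per scenario agrees: about 0.75, 0.50 and 0.25.

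**4. Patients moved over a cut-point.** The share moved at 65 is approximately P(true full age = 64) × share overstated; at 75, use 74. For mean 70 and SD 10:
- P(64 ≤ age < 65) = Φ(−0.5) − Φ(−0.6) = 0.3085 − 0.2743 = 0.0342
- × 0.75 = 0.026, and × 0.25 = 0.009

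The simulation gives, per 100 patients (at 65 / at 75):

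| Procedures in | 70/10 | 68/12 | 72/8 |
|---|---|---|---|
| January–June | 2.55 / 2.73 | 2.38 / 2.17 | 2.38 / 3.53 |
| April–September | 1.70 / 1.84 | 1.63 / 1.39 | 1.65 / 2.36 |
| July–December | 0.88 / 0.89 | 0.81 / 0.68 | 0.81 / 1.17 |

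The range is about 0.8 to 2.6 per 100 at 65, and about 0.7 to 3.5 per 100 at 75.

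**5. After the fix.** With a calendar-year difference and a month-and-day comparison, the rule returns the exact full age for every patient, and none crosses a cut-point wrongly.

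**The case against.** The strongest reply is that the intent is plain. The section names full age as its target, and a subtract-1 step serves that target only as a birthday comparison, so a competent programmer would code it that way. The SAP also reads as a translation: a Japanese label survives in the termination table of 3.3.4, and the day-count formula in 4.4.1 contains a spelling slip. Writing date of birth for birthday would be an error of the same kind. This largely stands. A slip is the likely explanation, and the documents do not show that any age has been or will be computed wrongly. It does not remove the point, because no other visible text supplies the month-and-day comparison.

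A second reply is that step 1 has no unit and could mean elapsed years, in which case no patient is misplaced. That also stands, so every figure above is conditional on the calendar-year reading.

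A third is that the consequence is slight. The visible text of SAP 8.2 specifies counts and incidences with no test, and the patency definitions and the 30-day analysis in 8.1 do not use age. This is correct and sets the severity.

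A reader might go further and infer that about half of all patients will be aged a year too old. The documents do not support that. It needs the calendar-year reading and also procedures balanced around mid-year or spread evenly over a full year, whereas enrolment lasts about 6 months in unstated months. A reader might also infer that a summary of patient age is biased, but no such table is visible in the SAP; Protocol 8.1 only lists age as a collected item.

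**Conclusion.** The point holds as a minor defect of specification. The correction step cannot operate as printed, and the unit of the difference is missing. Whether this produces wrong ages depends on how step 1 is programmed, which the documents do not settle.

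On the calendar-year reading, the rule overstates age by one year in about a quarter to three quarters of patients. At the target of 100 indicated cases, about one to three patients would move at 65 and about one to four at 75, always into the older group. The first range rests on evenly spread birthdays and procedures within a 6-month window; the counts rest in addition on the assumed age distributions. On the exact elapsed-years reading, no patient is misplaced. Only the age-split tables in SAP 8.2 are exposed.

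**What to change.** Replace the two steps in SAP 4.4.4 with: *Age = year of procedure minus year of birth; subtract 1 if the month and day of the procedure are before the month and day of birth.* This settles the unit and the comparison together.

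Then check that the program deriving age follows this rule. If it does, nothing else changes. If it does not, rerun the age-split tables in SAP 8.2.

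The cost is one sentence and a short program check. No new data are needed, because the study form already holds the date of birth and the procedure date.
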